9.3.2 ANALYSIS OF THE PRIMARY EFFICAY ENDPOINTS

The primary endpoint of the study is the mean improvement from baseline in EASI versus the follow-up visits (months 3-12). The comparison of improvement in EASI will incorporate all available post-intervention follow-up visits. Our primary goal will be to compare the mean difference in improvement between groups to examine if they are equivalent.

We will use an intent-to-treat (ITT) approach to evaluate equivalency of changes between the two arms across 12 months for AD-disease-severity and quality-of-life endpoints using longitudinal linear mixed modeling. This modeling allows us to account for intra-individual variability and the possibility of different numbers of follow-up measurements inherent in this pragmatic research design. For these analyses, the null hypothesis is that there is a differential treatment effect between the groups: H_0 : $\mu I_{n-person} \neq \mu_{TCH}$. The alternate hypothesis is H_A : $\mu_{In-person} = \mu_{TCH}$, where μ represents the average change from baseline across the follow-up visits (3 months – 12 months).

For the primary comparison of baseline versus average of follow-up visits, a dummy-coded time variable will be coded with 0 = baseline and 1 for all follow-up visits, so that the estimate of the effect will indicate the difference between baseline and the average of follow-up visits. In addition, a group

variable will be added to the model (coded 0 for in-person and 1 for TCH) along with a group x time effect.

We consider $\delta_0 = \pm 6.5$ as the equivalence limit for the primary endpoint of EASI. This equivalence limit of 6.5 was selected for EASI because it represents the minimal clinically important difference in the AD literature.²⁸ It is also more conservative than equivalency limits of 12-20 from pilot studies.²⁹

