3 OBJECTIVES AND ENDPOINTS

OBJECTIVES	ENDPOINTS	JUSTIFICATION FOR ENDPOINTS
Primary		
Aim 1: Compare differences in atopic dermatitis disease severity, as measured by Eczema Area and Severity Index (EASI), and validated Investigator Global Assessment (vIGA), and Patient-Oriented Eczema Measure (POEM) between patients randomized to TCH and in-person care in a 12-month pragmatic, randomized equivalency trial.	 The primary endpoint of the study is the mean improvement from baseline in EASI averaged across 12 months. The mean improvement in EASI is defined as the difference in EASI between baseline and the average of the follow-up visits (months 3-12). Secondary endpoints for Aim 1 include: Change in vIGA from baseline averaged across 12 months Change in POEM from baseline averaged across 12 months 	EASI is a validated, granular assessment of AD patient disease severity. It is commonly used in clinical trials, including trials for therapeutic approvals. By using EASI, we will be able to compare the results of this study with other studies in AD patients. The 5-point IGA is a valid measure of disease severity and meets the need for a clinically meaningful measure for atopic dermatitis. POEM is a validated patient-reported outcome used to

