9.3 STATISTICAL ANALYSES

9.3.1 GENERAL APPROACH

For this pragmatic, randomized trial, we will compare patients randomized to the online, team-based connected health (TCH) versus patients receiving in-person care across one year. The overall analytical strategy is to use linear mixed or generalized estimating equations, depending on the outcome variable, to account for repeated measures within patients. Random effects for patients will be included in the model so that the estimates of any patient-level variables will be appropriately calculated. Additionally, we will adjust *a priori* for the randomization stratification factors site and age group (<18 years, and 18+ years) in all models. While we do not anticipate a site-level main effect, random effects for site will be included in the model in case there are factors common to patients within a site that affect the outcome.

For comparison of AD disease severity (Aim 1) and quality of life (Aim 2), we will test an equivalence hypothesis between the interventions using longitudinal linear mixed effects modeling; this allows for the estimation of intra-individual variance. Using this same technique, we will test the hypothesis of improved access to specialist care (Aim 2) and cost-saving (Aim 3) with the TCH model compared to the in- person model.

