9.3.3 ANALYSIS OF THE SECONDARY ENDPOINTS

Analysis of Disease Severity (Aim 1)

In Aim 1, we will assess a secondary endpoint, vIGA, which is an ordinal scale that provides a global assessment of the patient's AD disease severity. vIGA is scored on a 5-point ordinal scale ranging from 0 (clear) to 4 (severe). We will apply the same general modeling procedure using generalized estimating equations with the ordinal outcome of vIGA. The reference category will be 0 = clear. The equivalence margin for vIGA is 0.5, which is smaller than the minimal clinically important difference and considered a conservative equivalence margin by AD experts.

We will also assess a secondary endpoint of patient-reported symptoms using the validated instrument POEM. For POEM, we will use the same modeling method as the one described for EASI. The scores for the POEM instrument range from 0 to 28. The equivalence margin for POEM is 3.4, which is the minimal clinically important difference defined in the AD literature.²⁸

Analysis of Health-Related Quality of Life and Access-to-Care Measures (Aim 2)

In Aim 2, we will compare health-related quality of life between patients from practices randomized to the two interventions. The hypothesis is that the TCH model results in *equivalent* improvement in health-related quality of life as that in the in-person arm, as measured by DLQI and Children's DLQI (CDLQI), and EQ- 5D-5L/EQ-5D-Y.

DLQI and CDLQI are validated dermatology-specific quality-of-life instruments for adults and children, respectively. The scores range from 0 to 30, with higher scores indicating more severe impact on quality of life. The equivalence margin for DLQI and CDLQI is \pm 4, which corresponds to the established minimal clinically important difference.²⁹

EQ-5D-5L and EQ-5D-Y are valid and reliable, generic preference-based quality of life instruments. In dermatology, EQ-5D-5L has been used in numerous AD trials. The equivalence margins for the utility index (\pm 0.15) and VAS (\pm 10) of the instrument are no larger than half of SD (Cohen's d = 0.5) and are considered the minimal clinically important difference.

The same repeated-measures, equivalency-evaluation approach described above for Aim 1 "Analysis of Atopic Dermatitis Disease Severity" will be used to compare responses to DLQI/CDLQI, and EQ-5D-5L/EQ-5D-Y between patients from practices randomized to the TCH model and in-person care across time.

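### The primary EASI model compares raw change with a free baseline arm difference; using the collected baseline efficiently would narrow the equivalence interval at almost no cost.

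*Combined protocol and SAP*

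**What the plan says.** Section 9.3.2 fits a longitudinal linear mixed model to EASI in which "a dummy-coded time variable will be coded with 0 = baseline and 1 for all follow-up visits". A group "variable will be added to the model (coded 0 for in-person and 1 for TCH) along with a group x time effect". The group x time coefficient is the arm difference in change from baseline, and the group coefficient is the arm difference at baseline. The section adds that "The comparison of improvement in EASI will incorporate all available post-intervention follow-up visits".

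Section 9.3.1 states that "Random effects for patients will be included in the model" and adjusts for "the randomization stratification factors site and age group (<18 years, and 18+ years) in all models". Neither section adds baseline EASI as a covariate or constrains the arms to a common baseline mean. Section 9.3.3 names baseline EASI as a covariate only for out-of-pocket costs.

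Section 3 defines the primary endpoint as baseline against the average of the month 3-12 visits. Section 9.3.3 carries the method to other outcomes: "For POEM, we will use the same modeling method as the one described for EASI", and "The same repeated-measures, equivalency-evaluation approach described above for Aim 1" is used for DLQI/CDLQI and EQ-5D.

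**The concern.** Allocation is randomised 1:1, so any arm difference in baseline EASI is due to chance. The planned model spends information on estimating it and subtracts the whole of it from the follow-up difference. Full subtraction is efficient only if mean follow-up EASI moves one for one with baseline. With a weaker relation it adds noise.

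The site and age-group terms do not recover the loss. As main effects they cancel from a within-patient change.

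Equivalence depends on whether the confidence interval lies inside ±6.5. A wider interval lowers the chance of showing equivalence when it is true, most of all near the top of the SD range in section 9.1 or if the arms differ slightly.

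**Working it through.** **Inputs from the documents.** Margin ±6.5 (9.1, 9.3.2); one-sided alpha 0.05, SD 15-20, 15% attrition, 272 sufficient and 300 enrolled (9.1); 1:1 allocation (5.4.1); one baseline and four follow-up visits (1.3).

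**Assumptions.** The documents do not give the within-patient correlation rho, and do not say whether the SD is for a single visit or for change. I take compound symmetry, 150 per arm, 3.75% lost before each follow-up visit (15% in all), and all available visits used.

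**The plan's own figure.** A single one-sided test at SD 20 gives n = 2 x [20 x (1.645 + 0.842)/6.5]^2, rounded up to 118 per arm, or 236; 236 x 1.15 = 271.4, that is 272. Two one-sided tests (TOST) at SD 17 also give 118 per arm. TOST at SD 20 needs 163 per arm, or 326/0.85 = 384 randomised. So 272 leaves no spare precision at the top of the SD range.

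**Closed form, complete data.** Let s be the single-visit SD and n the number per arm.
- Planned contrast: variance = (2/n) s^2 [(1+3rho)/4 + 1 - 2rho] = (2/n) s^2 x 1.25(1-rho).
- Baseline-adjusted contrast: variance = (2/n) s^2 [(1+3rho)/4 - rho^2] = (2/n) s^2 x (1-rho)(1+4rho)/4.
- Ratio, adjusted to planned: (1+4rho)/5, that is 0.44, 0.60 and 0.76 at rho 0.3, 0.5 and 0.7.

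Simulation with 255 complete patients at SD 17.5 gave ratios of 0.437 and 0.601 at rho 0.3 and 0.5. The planned estimate equalled the raw difference in mean change to four decimals, even with age group in the model.

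**With dropout.** Expected generalised-least-squares information, single-visit SD 20. Half-width = 1.650 x SE, from t on 298 df. Arrows run from the planned to the adjusted model.

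| rho | SE | Variance ratio | 90% CI half-width | TOST power, true difference 0 | TOST power, true difference 2 | Planned-model N for equal precision |
|---|---|---|---|---|---|---|
| 0.3 | 2.20 → 1.49 | 0.460 | 3.6 → 2.5 | 81% → 99% | 64% → 91% | 300/0.460 = 652 |
| 0.5 | 1.87 → 1.47 | 0.618 | 3.1 → 2.4 | 93% → 99% | 78% → 92% | 300/0.618 = 485 |
| 0.7 | 1.45 → 1.28 | 0.773 | 2.4 → 2.1 | 99.5% → 99.9% | 93% → 97% | 300/0.773 = 388 |

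At the ends of the range the ratio is 0.299 (rho 0.1) and 0.926 (rho 0.9).

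**Single-visit SD 15.** Planned power at zero difference is already about 98% or more at rho 0.3 to 0.7. Half-widths still fall: 2.7 to 1.8, 2.3 to 1.8 and 1.8 to 1.6.

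**SD 20 read as the SD of change to the follow-up average.** The single-visit SD is then 20/sqrt[1.25(1-rho)]. Planned power is 73.5%, 73.0%, 72.5% and 72.3% at rho 0.3, 0.5, 0.7 and 0.8 (half-width 3.9). Adjusted power is 98.5%, 93.6%, 85.8% and 81.3%. Adjusted half-widths at the first three are 2.6, 3.1 and 3.4.

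**Source of the gain.** Deleting only the baseline group term gives ratios of 0.460, 0.617 and 0.772. Baseline as a covariate gives 0.460, 0.618 and 0.773. Categorical visits with the group term kept give 1.001. The gain comes from the handling of baseline, not from the visit coding.

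**The case against.** The strongest reply is that nothing is broken. The planned model is a recognised one, unbiased for the stated endpoint, and the gain depends on quantities the documents do not give. Much of that is right.

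- **Power is often adequate already.** With a single-visit SD of 20 and zero true difference, the planned model reaches 80% at rho 0.3, 0.5 and 0.7, though only 67% at rho 0.1. On the SD-of-change reading, planned power is 95-96% at SD 15 and 86-87% at SD 17.5. The 73% belongs to the top of the range on one reading, where the implied single-visit SD is 21, 25 and 33 at rho 0.3, 0.5 and 0.7.
- **The gain fades at high correlation.** At rho 0.9 the variance saving is 7%, and on the SD-of-change reading at SD 20 power goes only from 72% to 77%.
- **Baseline must precede allocation.** The schedule places randomisation and baseline EASI together at Month 0 with a 28-day window and no stated order. EASI is listed as patient-reported, and patients are not blinded. If knowing the arm shifted every score by 2 points, raw change would cancel it and the adjusted contrast would carry 2(1-rho). If it shifted baseline only, raw change would carry all 2 points and the adjusted contrast 2rho. Neither model dominates, and nothing shows that baseline follows allocation, but the order deserves a sentence in the SAP.
- **A smaller edit would do.** Under compound symmetry, deleting the group term gives the whole gain. That relies on the random-intercept structure being right. An unstructured covariance and equal visit weights avoid that reliance and keep the section 3 endpoint.

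These points limit the size of the gain. They do not remove it: in large samples the adjusted contrast is never less precise than raw change.

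**Conclusion.** The concern holds, as a matter of precision and not of bias or of a wrong endpoint. The planned interval is wider than the collected data require unless mean follow-up EASI tracks baseline one for one. The variance saving is 54%, 38% and 23% at rho 0.3, 0.5 and 0.7, and 70% to 7% over rho 0.1 to 0.9. What this means for power ranges from negligible (single-visit SD 15) to the difference between missing and meeting the 80% target (SD of change 20, rho up to about 0.8).

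Confidence is high on direction and moderate on size. The size rests on assumed correlation, compound symmetry, evenly spread dropout and the reading of the SD. The planned power on the SD-of-change reading also depends on how dropouts are counted: 73% uses all available visits, and 66% counts only 255 completers. The change should be made because it costs so little.

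**What to change.** In section 9.3.2, specify one of two models.

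1. **Common baseline mean.** Keep baseline EASI as an outcome row and remove the baseline group effect. Use categorical visit, arm-by-visit terms at months 3, 6, 9 and 12 only, and an unstructured within-patient covariance in place of the patient random effects.
2. **Baseline as covariate.** Model months 3-12 only, with baseline EASI and baseline-by-visit terms. This omits patients with no follow-up visit.

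Baseline should not be a covariate while it is also an outcome row. In either model, estimate the equally weighted mean of the four visit-specific arm differences and compare its 90% CI with ±6.5. Keep the planned site and age-group adjustment, and state that baseline EASI is recorded before allocation is revealed.

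Use the same baseline handling for POEM, DLQI/CDLQI and EQ-5D, with a simpler covariance where age-specific instruments leave small subsets.

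The cost is SAP wording and a few lines of code, with no new data, visits or patients. The one technical price is that the first model estimates 15 covariance parameters. In simulation at SD 20 with the same dropout, its error rate at a true difference of 6.5 was 4.8-5.4% (10,000 trials per setting, including unequal correlations). Power at zero difference was 99.2%, 99.4% and 99.98% at rho 0.3, 0.5 and 0.7 (5,000 trials each).

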5.4.2 RETENTION PLAN

Prior to study initiation, we will conduct pre-trial retention training for the study staff. Prior to enrollment, the study staff will communicate with eligible patients regarding the importance of completing all outcome assessments. We will emphasize the importance of full participation during screening, enrollment, and throughout the trial.

It is important to note that, for online and in-person visits between the provider and patients, these visits occur at an individualized frequency based on medical necessity. However, the collection of outcome assessments (disease-severity, quality-of-life endpoints, and selected access-to-care measures) occurs at a quarterly basis for all participants.

All subjects will be reminded via email, text, or telephone to submit their quarterly outcome assessments beginning 7 days prior to the due date. If a subject fails to submit the quarterly outcome assessments within 2 days of the due date, the subject will be contacted using telephone and/or electronic methods to remind them to submit the assessments. The study staff will also discuss with the participant strategies to improve adherence with the study requirements. If the participant cannot be contacted after at least five attempts, a certified return receipt letter will be sent to encourage continuation in the trial.

If a participant fails to complete a quarterly assessment within 21 days of the due date, the study staff will make at least five attempts to contact (at least three telephone calls, two emails, and, if necessary, a certified return receipt letter to the participant's last known mailing address or local equivalent method). These contact attempts will be documented in the participant's study file.

If a participant wishes to withdraw from the study, the study coordinators will attempt to collect the Month 12 visit data as well as detailed data on the reasons for the discontinuation from the study. The study coordinators are encouraged to share their ideas and experiences to promote participant retention via regular communication during staff meetings.

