7.2 PARTICIPANT DISCONTINUATION/WITHDRAWAL FROM THE STUDY

The study team will ensure that participants are fully informed and understand the study commitments as presented in the informed consent form to minimize patient withdrawal. Patients are encouraged to complete the study regardless of their response. Participants may withdraw from the study at any time without impact to their care. In the event a participant discontinues study treatment before study completion, the study team will attempt to collect the Month 12 visit data. They may also be discontinued from the study at the discretion of the PI if patient's participation poses a safety concern to himself/herself or to the study staff.

The reason for participant discontinuation or withdrawal from the study will be documented on the Enrollment Status eCRF. Subjects who sign the informed consent form and are randomized and receive the study intervention, and subsequently withdraw, or are withdrawn or discontinued from the study will not be replaced, nor will they be eligible for rescreening.

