7.3 LOST TO FOLLOW-UP

All attempts will be made to minimize lost to follow-up. A participant will be considered lost to follow-up if he or she fails to complete a quarterly assessment according to the Schedule of Activities within 6 weeks of scheduled date of completion.

If a participant fails to complete a quarterly assessment within 2 days of the due date, the subject will be contacted by phone and electronically to submit the assessments. The study staff will also discuss with the participant strategies to improve adherence with the study requirements.

If a participant fails to complete a quarterly assessment within 7 days of the due date, the following steps to will be initiated:

- The study staff will make *at least* five attempts to contact (at least three telephone calls, two emails, and, if necessary, a certified return receipt letter to the participant's last known mailing address or local equivalent methods.) These contact attempts will be documented in the participant's study file.
- Should the participant continue to be unreachable within 6 weeks of the scheduled date of completion, he or she will be considered to have withdrawn from the study with a primary reason of lost to follow-up.
- The Principal Investigator will have the ultimate discretion on the final determination of whether additional attempts should be made to contact the participant or if the participant should be declared lost to follow up.

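### With incomplete follow-up, the primary model's single 0/1 time code averages whichever EASI visits were observed, not the equally weighted Month 3-12 average that defines the endpoint

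*Combined protocol and SAP*

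**What the plan says.** Section 3 sets the target: "the difference in EASI between baseline and the average of the follow-up visits (months 3-12". Section 5.4.2 fixes the schedule, since outcome collection "occurs at a quarterly basis for all participants", so the target is an average over Months 3, 6, 9 and 12.

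Section 9.3.2 sets the model. It states that "a dummy-coded time variable will be coded with 0 = baseline and 1 for all follow-up visits", and adds a group indicator and a group x time term. Section 9.3.1 adds patient and site random effects and the stratification factors. No section adds a visit term, time since baseline, or a weighting of visits.

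On incomplete data, section 9.3.2 says: "The comparison of improvement in EASI will incorporate all available post-intervention follow-up visits". It adds that the mixed model accounts for "the possibility of different numbers of follow-up measurements inherent in this pragmatic research design". No missing-data method or sensitivity analysis is given for EASI.

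Two rules shape which visits are observed. For early discontinuation, section 7.2 says "the study team will attempt to collect the Month 12 visit data". For a participant still unreachable six weeks after a missed assessment, section 7.3 says "he or she will be considered to have withdrawn from the study with a primary reason of lost to follow-up", subject to the investigator's discretion.

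**The concern.** A patient random effect deals with how many visits a patient supplies. It does not deal with which months they are. With one follow-up level per arm, the model treats a Month 3 value and a Month 12 value as measurements of the same mean. If EASI is still moving between Months 3 and 12, an arm that loses late visits has its mean pulled towards the early values.

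The primary conclusion rests on the group x time estimate and its interval against ±6.5. A shift towards zero raises the risk of a false claim of equivalence, and a shift away from zero costs power. Nothing in the planned EASI analysis would reveal either. Section 9.3.3 carries the same approach to POEM, DLQI/CDLQI and EQ-5D.

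**Working it through.** **Inputs from the documents:** margin ±6.5 (9.3.2); 15% attrition, SD 15-20, one-sided alpha 0.05, 300 enrolled (9.1); 1:1 allocation (5.4.1). The plan gives no figure for this bias, so there is none to reproduce.

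**Assumptions:** improvement at Months 3/6/9/12 of 3/5/6/6, 2/5/8/10 or 4/8/10/12, the same in both arms, so the true difference is 0. These courses change by 3, 8 and 8 points after Month 3. Within-patient correlation r is 0.5 to 0.7. Baseline is always observed, and missingness depends on arm but not on outcome.

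**Formula.** Under a patient random-intercept model with the 0/1 code, the expected change in an arm is a weighted mean of the pattern averages. A pattern held by a proportion p of the arm, with m follow-up visits, has weight p x m/(1 + m r). A direct generalized least squares calculation gives the same values.

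**Complete data.** There is one pattern, so the estimate is the plain average. For 4/8/10/12 it is 34/4 = 8.5, which is the section 3 endpoint.

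**Worked case.** Course 4/8/10/12, r = 0.5, 15% of TCH lost after Month 3, in-person complete:
- complete TCH patients: weight 0.85 x 4/3 = 1.1333, average 8.5
- lost TCH patients: weight 0.15 x 1/1.5 = 0.1, average 4
- TCH estimate: (1.1333 x 8.5 + 0.1 x 4)/1.2333 = 8.135
- in-person estimate: 8.5, so the false difference is 0.36.

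**Results** (in-person minus TCH improvement; positive makes TCH look worse; ranges are for r = 0.5 to 0.7):

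| Pattern, TCH / in-person | 3/5/6/6 | 2/5/8/10 | 4/8/10/12 |
|---|---|---|---|
| 20% / 10% lost, spread evenly after Months 3, 6, 9 | 0.07 to 0.08 | 0.19 to 0.20 | 0.19 to 0.20 |
| 20% / 10% lost, all after Month 3 | 0.12 to 0.13 | 0.25 to 0.27 | 0.26 to 0.29 |
| 15% lost after Month 3 / none | 0.16 to 0.18 | 0.34 to 0.38 | 0.36 to 0.40 |
| 15% / 15% lost after Month 3 | 0 | 0 | 0 |
| 20% with Months 3 and 12 only / complete | 0.08 | 0.04 | 0.08 |
| Stress: 20% Month 12 only / 25% lost after Month 3 | -0.40 to -0.44 | -1.02 to -1.13 | -1.03 to -1.14 |

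A flat course gives 0 for any pattern. A waning course (10/8/6/4) reverses the sign.

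**Equal patterns, different courses.** Take TCH 8/8/8/8 and in-person 4/8/9/11; both average 8. With 15% lost after Month 3 in each arm and r = 0.5, the in-person estimate is (1.1333 x 8 + 0.1 x 4)/1.2333 = 7.68, a false difference of 0.32 in favour of TCH.

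**Consequence.** With 300 x 0.85/2 = 127.5 per arm, the standard error is SD x sqrt(2/127.5): 1.88 at SD 15 and 2.50 at SD 20. If the true difference lies at the margin, a bias b towards zero changes the one-sided 5% error to about Phi(-1.645 + b/SE):
- b = 0.29: 6.8% (SD 15) or 6.3% (SD 20)
- b = 0.40: 7.6% or 6.9%
- b = 1.14: 15% or 12%

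**Under the fix.** With visit as a category and an equal-weight contrast, the expected bias is 0 in all these cases. A simulation with 30% of TCH dropping out after Month 3, at random or depending on Month 3 EASI, used rising courses 3/5/7/8, 4/8/10/12 and 2/6/10/14. The average error was 0.45 to 1.09 for the pooled code and within ±0.06 for the categorical model.

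**The case against.** The strongest reply is that the effect is small at the attrition the plan expects. Even with a 2:1 imbalance it is at most 0.29 points, or 0.29/6.5 = 4.5% of the margin and about 0.12 to 0.15 of a standard error. That stands, and it limits the priority of the point.

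Three stronger readings are tempting, and the documents do not support them.

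- A reader might infer from section 7.1 that visit patterns are likely to differ by arm, because stopping criteria are listed only for the online intervention. Those criteria concern the intervention, not outcome collection. Section 5.4.2 keeps quarterly assessments for everyone, with remote reminders in both arms, and section 7.2 encourages completion. In an open-label trial a difference is plausible, but it is not shown to be likely.
- A reader might infer that section 7.2 produces many patients with Month 12 only. Visits supplied before stopping stay in the analysis, so that pattern requires stopping before Month 3 and returning at Month 12. A patient who stops after Month 3 and returns supplies Months 3 and 12, which gives only 0.04 to 0.08.
- A reader might take about 1.1 points, some 18% of the margin, as the expected bias. It needs opposite patterns in opposite arms, a steep course, and (20% + 25%)/2 = 22.5% incomplete against the planned 15%.

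The reply does not remove the mismatch between the endpoint and the estimator.

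**Conclusion.** The point holds as a conditional bias. The estimator matches the section 3 endpoint if data are complete, if EASI is flat after Month 3, or if both visit patterns and time courses are the same in the two arms. Otherwise it can be biased in either direction, even when missingness is unrelated to outcome within each arm.

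Under the assumed courses, the likely size near planned attrition is a few tenths of a point or less, and about 1.1 is a stress value. All sizes rest on courses and correlations that the documents do not give. The claim in section 9.3.2 about different numbers of measurements is not simply false, since it holds when patterns and courses are alike; it does not hold in general. The change is worth making because it is cheap and removes a dependence that the plan does not check. No change in sample size follows from this point.

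**What to change.** In section 9.3.2, replace the 0/1 time code with categorical visit (0, 3, 6, 9, 12) and group x visit. Define the primary contrast as the equally weighted average of the four follow-up group differences in change from baseline. Compare its confidence interval, at the level matching the one-sided 5% in section 9.1, with ±6.5. Use the same contrast for POEM, DLQI/CDLQI and EQ-5D.

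The cost is SAP wording and one contrast statement. The mean model grows from 4 to 10 arm-by-time parameters, six more, which is negligible with about 300 patients. The data are already scheduled. The change does not correct for dropout that is not at random; that would need its own sensitivity analysis.
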